#### Figure 2. Outcome measures at testing day 1 and 2.

The first testing day: Once participants arrive at the lab, they will complete health questionnaire, including the Foot and Ankle Ability Measures (FAAM). Then, they will be asked to do 5~10 minutes of a warm-up. After the warm-up, the investigator will assess double leg balance and a single-leg balance. The static postural control testing requires 3 successful trials of balance for each task. During the static postural control assessment, concomitant assessments of ankle muscle activation (soleus, fibularis longus, and tibialis anterior) will be assessed. Once a participant finishes the static postural control assessment, neural excitability testing will be performed in the counterbalanced order of TMS and H-reflex to prevent the order effect. The second testing day: Once participants arrive at the lab, they will be asked to do the warm-up. After the warm-up, participants will perform dynamic postural control tests (star excursion balance test and side hop). The detailed procedures for each outcome measure are described in the following subsections.

#### **Outcome Measures**

Spinal Excitability (H-reflex): The cathode (2 mm shield disk electrode, BIOPAC Systems Inc., Goleta CA, USA) will be secured over in the superior popliteal fossa proximal to the bifurcation the tibial and common peroneal nerve with a strip of hypoallergenic tape and the dispersive electrode (circular carbon-impregnated dispersive pad) will be positioned on the anterior thigh just above the patella. The soleus H-reflex will be elicited by a 1-ms square-wave electrical stimulus applied to the sciatic nerve at increasing intensities until a maximal Hoffmann reflex (H-reflex) and maximal motor response (M-response) are found. The soleus muscle was selected due to its functional role in postural control. Five maximal H-reflex and M-response measurements will be recorded. The averages of both responses will be used to calculate the Hmax/Mmax ratio as an outcome variable representing the spinal excitability. Corticospinal Excitability (TMS): The participant will be accustomed to the stimulus by progressively increasing the TMS stimulator (Magstim Company Ltd, Wales, UK) intensity up to the intensity that results in motor response. The participant may feel minimal sensations at the point of application (like a puff of air on the scalp). After a brief introduction of the stimulation, participants will be asked to wear a Lycra swim cap that has a dot grid line (1cm x 1cm squares) and a straight line in the middle sagittal plane in order to navigate the brain area. A series of TMS stimuli of 1.0 Tesla will be delivered to identify the location of the motor cortex where the investigator observes the largest amplitude (hotspot). Once the hotspot is determined, a magnetic field will be introduced to the scalp at a location in the primary motor cortex where cortical neurons innervating the soleus muscle are located. When the magnetic field is received at the primary motor cortex at the appropriate area, motor signals are sent to the soleus muscle. We will record these signals with surface electrodes that are on the soleus muscle. As the intensity of the TMS increases, the soleus muscle will briefly contract/twitch that is known as motorevoked potential (MEP). The contraction is comparable to what would be felt during standard medical reflex testing. The active motor threshold (AMT) will be defined as the stimulator intensity required to elicit a peak-to-peak MEP amplitude above 3 standard deviations of mean soleus EMG activity during10-sec of both single and double leg stance. AMT will be determined by using a software that runs the

maximum-likelihood threshold tracking algorithm, Parameter Estimation by Sequential Testing (PEST). Ten trials of TMS will be delivered at two different TMS intensities of AMT110% and 120% in order to assess motor neuron activity at the supra-spinal level. TMS tests will be performed while participants maintain single and double leg balance. The averages of responses at each intensity will be used as an outcome variable representing the corticospinal excitability. Electromyography (EMG): For measurements of H-reflex and TMS responses, it requires EMG signals from muscles to be recorded. A total of 4 EMG Ag-AgCl electrodes will be placed over the lower leg muscles including soleus, fibularis longus, and tibialis anterior and the one reference electrode on the lateral malleolus. The surface EMG electrode will be placed based on the SENIAM recommendations. Static Postural Control: The static postural control will be measured at unipedal and bipedal stance on a force plate (Accusway Plus, AMTI, Waterfront, MA). For bipedal stance, participants will be asked to maintain a barefoot stance with their shoulder-width apart and crossed arms on the chest. The foot positions will be outlined with tape. Participants will be asked to stand as still as possible during testing. Participants will complete three trials of bipedal stance with eyes open and eyes closed condition for 10 seconds each trial. After the bipedal balance testing, the participant will be asked to perform unipedal balance testing. Participants will be asked to stand on their involved limbs of CAI. The stance foot will be put on the midlines of the forceplate. The participant will be asked to maintain their unipedal stance. Participants will complete three trials of unipedal stance with eyes open and eyes closed condition for 10 seconds each trial. If a participant touches down with the opposite limb, contacts the stance limb, or is unable to maintain standing posture during the 10-second trial, the trial would be terminated and repeated. Successful trials of each balance testing will be recorded. Dynamic Postural Control: Star Excursion Balance Test (SEBT): SEBT is a clinical assessment for functional deficits of lower extremity balance. Participants will be asked to stand barefoot on a firm surface. Participants will stand on a single leg with the CAI involved limb placed at the center of different lines (anterior (A), posteromedial (PM), postero-lateral (PL). Participants will be asked to reach the furthest point on the line with extending their contralateral foot. Participants will be asked not to move their stance foot from their center position, with hands on the hip. The distance from the center of the grid to the furthest reach point will be manually measured in cm with a measuring tape. Three testing trials with 4 practice trials will be performed with each participant in each direction on each side. The mean of three trials will be used for the analysis. Side Hop: All participants will be instructed to hop on their CAI-involved limbs. Participants will be instructed to hop laterally over a 30-cm distance by alternating sides from lateral direction back to the starting location with an involved limb. One repetition will be the ability to hop laterally and return to the starting location. Participants will be instructed to complete 10 repetitions as quickly as possible. Testing trials will be repeated until 3 successful ones. If a participant falls, put the contralateral foot on the ground, and do not follow the course outline, the trial will be considered "a failed trial." The examiner will record the total time to complete the trial, using the stopwatch, to the nearest 0.01 second. Participants will perform three practice trials, followed by 3 testing trials. The average of 3 testing trials will be recorded and used for analysis. Self-reported

> functions: The Foot and Ankle Ability Measure (FAAM) is a self-reported measurement designed to examine ankle function for patients with foot and ankle related impairments. FAAM is divided into two subscales, such as Activities of Daily Living (ADL) and Sports Subscale. The FAAM-ADL consists of 21-item questionnaire and assesses various ankle activities such as standing, walking, stepping, and squatting. The FAAM-Sports consist of 8-items questionnaire and assess more challenging activities related to sport such as running, jumping, landing, starting-stopping quickly, cutting movements and sports specific movement. Both FAMM-ADL and Sports will be administered to each of participants. The investigator will guide participants how to fill out the ankle questionnaire. Once participants complete the questionnaire, the investigator will score each questionnaire. Each item is scored on a 5-point scale from "no difficulty at all" being 4 points to "unable to do" being 0 points. The total score for FAAM-ADL is 84, and FAAM-Sport is 32, which will be transformed into percentage scores. A higher percentage represents higher levels of ankle function. These percentage scores provide perceived ankle dysfunction in patients with CAI. The FAAM is a reliable and valid measure for patients with CAI.

#### **Study Interventions**

Transcranial Direct Current Stimulation: Participants in the active and sham tDCS groups will receive tDCS while performing balance exercises (about 20-min application). An anodal surface electrode will be attached to the contralateral motor cortex (M1) of the CAI-involved side and the reference electrode will be placed on the ipsilateral side of the supraorbital ridge. These electrode placements (stimulation sites) were consistent with previous studies.[39, 40] Anodal tDCS will deliver a low electrical current stimulation at 2 mA, while for sham tDCS, the stimulator will be turned off automatically 30 s following the application. The sham stimulation mimics the transient scalp sensation perceived when the stimulator is initially switched on. This technique is currently state-of-the-art for conducting convincing sham stimulation in the tDCS field. For tDCS treatment set-up, participants will sit on the chair. Sponge electrodes will be placed and secured with a head strap: Active electrode over the motor cortex area and the reference electrode on the contralateral side of the upper forehead. The tDCS set-up will take approximately 10 minutes. Participants will undergo 12 sessions (20-min each) of active or sham tDCS using 2mA current. This constant current device ramps up to the desired amplitude and ramps the amplitude back to 0mA at the end of the treatment duration. tDCS (real or sham) will be delivered from beginning of balance training to the end of the training. After each training session, an aloe cream will be applied to the skin under the electrodes to reduce risks associated with skin drying. **Balance training:** All groups will receive the same progressive balance training (BT). BT will be implemented 3 times a week over 4 weeks, each training session lasting about 20 minutes. The 4 weeks of BT has been shown effective in enhancing postural control in patients with CAI. The BT will consist of 3 types of balance exercises: (A) single-leg stance exercise with eyes open and closed and on stable and unstable surfaces, (B) single-leg deadlift exercise with eves open and on stable and unstable surface, and (C) balance

exercise on wobble board. Participants will be asked to perform a progressive level of exercise in each session.

The single-leg exercise is static balance exercise. Participants will be instructed to maintain their single leg balance with their CAI involved limb as still as possible. There will be 6 levels of difficulty. Participants will advance to the next level if they demonstrate error-free performance. The error includes falling, touching down with the opposite limb, bracing the non-stance limb against the stance limb, and opening the eyes during the eyes-closed condition.

Single leg deadlift is a semi-dynamic balance exercise that involves a hip-hinge movement while maintaining a single-leg balance. Participants will be instructed to stand with their feet hip-width apart and parallel, Then, they will be asked to lean forward in their torso by shifting the weight onto the involved leg while the nonweight bearing leg extends backward. The extended leg will be lifted, and the torso will be shifted forward until the "T" shape is formed. There will be 6 levels of difficulty. Participants will advance to the next level if they perform the deadlift without errors including excessive trunk motion (more than 30 degrees of lateral flexion), removing the hands from the hips for the related activities, and missing the target.

The wobble board exercise is a dynamic balance exercise. The wobble board is a circular plate (30 inches) with different sides of domes that screw into the bottom of the board to make balance exercises challenging. Participants will perform the exercise near a wall and be only allowed to touch fingertips to the wall for stability. A balance exercise will be performed on the board, and then clockwise and counterclockwise rotations of the rim of the board will be completed. The dome with the shortest diameter will be considered the lowest level (e.g., level 1) and all participants will begin performance on this level. Five levels will be used for training, and height of each level increased by half inches. Thus, heights ranged between 1 and 3 inches. The initial direction of rotation will be selected by participants and will be changed every 10 seconds of the 40-second trial. There will be 5 difficulty levels. Participants will be progressed to the next level if they perform balance on the board with smooth transitions between and within rotation directions as well as self-reported feelings of "easiness.

# 6) Data and Specimen Banking\*

All data collected from this study will be stored on password protected computers at the Sports Medicine Laboratory in the Max Orovitz Building. Participants will be assigned own identification number at the time of participation. Our laboratory is in a locked building with limited key card swipe access. Only investigators for this study will have access to the data.

# 7) Data Management\*

Data will be stored in a personal computer which is in locked research offices and is encrypted and password protected. The means and standard deviations will be calculated for one pre and two post outcome measures and will be used for statistical analysis. The normal distribution of data will be assessed by using the Shapiro-Wilk tests. For each outcome measures (postural control, neural measures, and self-

> reported function), 2 (group: anodal tDCS+BT and sham tDCS+BT) by 3 (time: preintervention, 2 weeks post-, 4 weeks post-intervention) ANOVA with repeated measures will be performed to determine effects of tDCS for each outcome measure. In the presence of a significant group-by-time interaction, a post-hoc analysis using Sidak adjustment will be conducted. The level of significance will be set a priori at 0.05. All statistical analyses will be performed using SPSS 26.0 statistical software (SPSS Incorporated, Chicago, IL, USA).

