Transcranial direct current stimulation (tDCS) is an non-invasive electrical stimulation technique over the brain that safely influences the cortical excitability, and it is a painless and portable.[24-29] It is thought that a subtle electrical current (up to 2.0 mA) can induce facilitatory effects on cortical excitability of the primary motor cortex: The anodal (+) stimulation is known to increase cortical excitability while cathodal (-) stimulation decreases the excitability.[31-33] Given these positive outcomes and high applicability (safe, portable, and easy-to-use), tDCS has been extensively used in the neuroscience literature[34-38] to address neurological symptoms including impaired postural control and motor dysfunction in a wide range

of neurological patients such as stroke[38], Parkinson's disease[36], and spinal cord injury[37].

There are emerging interests in tDCS to address musculoskeletal conditions. A recent study [39] has examined its efficacy for patients with chronic low back pain and confirmed its effects on pain and postural control. Anodal tDCS was applied to the motor cortex area during 20 minutes of balance training: It was found that pain and postural control were significantly improved after the intervention (tDCS with balance training).[39] Besides, tDCS has been used in patients with CAI. The tDCS was applied to the patients before they began their strength training. The use of tDCS in combination with strength training was found superior to strength training alone CAI patients.[40] This tDCS study for CAI clearly shows that CAI patients are responsive, and raise the potential that tDCS can be incorporated into other CAI rehabilitation programs such as balance training. Thus, it is possible to hypothesize that BT with tDCS would improve postural control and patients reported outcome along with enhancement in neural excitability, which induces superior improvements to BT alone.

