# 5) **Procedures Involved\***

## **Study Overview**

The proposed study is a double-blinded, randomized-control design which examines the efficacy of tDCS with balance training (BT) for patients with chronic ankle instability (CAI). Participants will be randomly allocated to one of two groups including (1) anodal tDCS + BT and (2) sham tDCS + BT. Outcome measures allow us to measure effects on postural balance, neural functions, and self-reported physical function.

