## 15) Local Number of Subjects

Sixty human subjects with chronic ankle instability will be recruited and enrolled in the study. A statistical power analysis was performed to estimate sample size, based on the previous tDCS study [40] on CAI patients with similar dependent variables (e.g., corticospinal excitability). The effect size (f=0.55) in this study was large using Cohen's criteria. With an alpha=0.05 and power = 0.80, the projected sample size needed is approximately 8 participants for each group with a total of 24 CAI patients. Thus, the proposed sample size of 20 for each group with a total of 60 CAI patients will be more than adequate and should also allow for expected attrition.

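### Every outcome is tested in its own ANOVA at 0.05, with no primary outcome and no adjustment across outcomes; if tDCS adds nothing, at least one significant interaction has roughly a 20–54% chance

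*Combined protocol and SAP*

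**What the plan says.** Section 7 (Data Management) groups the outcomes as postural control, neural measures and self-reported function. It states that a 2 (group) by 3 (time) "ANOVA with repeated measures will be performed to determine effects of tDCS for each outcome measure". On the error rate it says: "The level of significance will be set a priori at 0.05". The only adjustment is this: "In the presence of a significant group-by-time interaction, a post-hoc analysis using Sidak adjustment will be conducted".

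No section ranks the outcomes. The Objectives and the Study Overview list three domains side by side, and the Study Overview describes the purpose as examining efficacy. The hypothesis at the end of the Background is that "BT with tDCS would improve postural control and patients reported outcome along with enhancement in neural excitability", without saying which of these decides. Section 15 (Local Number of Subjects) mentions corticospinal excitability only as an example of the variables in the earlier study, so the power calculation does not supply a primary outcome either.

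Within the domains there are several variables. For TMS, "The averages of responses at each intensity will be used as an outcome variable representing the corticospinal excitability", and the test is done in two stances. During static balance, "concomitant assessments of ankle muscle activation (soleus, fibularis longus, and tibialis anterior) will be assessed". No force-plate variable is named for static balance.

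**The concern.** A 5% level per test limits the error of one test. When many outcomes are each tested at 5% and any of them may carry the conclusion, the chance of a false positive somewhere grows with the number of tests. The Sidak step does not address this. It starts only after an outcome's interaction has been declared significant at 0.05, and it then corrects the comparisons within that outcome.

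The plan also does not say what result would show that tDCS adds to balance training. Without a deciding variable or a success criterion, nothing in it prevents a single chance interaction from being presented as efficacy. A reader of the results could not tell whether the reported outcome was the one the trial was built to test. The unnamed force-plate variable adds further room for choice after the data are seen.

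**Working it through.** **The plan's own figure.** The documents give no error rate across outcomes, so there is none to reproduce. The only computed design figure is the sample size in section 15: f = 0.55, alpha 0.05, power 0.80, 8 per group and 24 in total. A noncentral F calculation for a group-by-time interaction, with noncentrality f² × N × (times − 1), three groups and three times, reproduces N = 24 (power 0.84; N = 21 gives 0.77). That figure, like 20 per group with 60 in total, implies three groups, whereas the Study Overview and section 7 describe two. This is a separate matter to reconcile. It does not affect the result below, which hardly changes with group size.

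**Inputs.** Alpha is 0.05 per test (section 7). The count comes from the Outcome Measures text, with one variable per measured condition:

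| Measure | Variables |
|---|---|
| Hmax/Mmax ratio | 1 |
| MEP, 2 intensities × 2 stances | 4 |
| Static balance, 2 stances × 2 vision conditions | 4 |
| SEBT directions | 3 |
| Side hop time | 1 |
| FAAM subscales | 2 |
| **Total** | **15** |

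- Averaging MEP over stances: 1 + 2 + 4 + 3 + 1 + 2 = 13.
- Also averaging static balance over vision conditions and SEBT over directions: 1 + 2 + 2 + 1 + 1 + 2 = 9.
- Fifteen is not a ceiling. Analysing EMG for three muscles in four static conditions would add 12, making 27. Several force-plate variables would also add to the count.

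**Independent tests.** The chance of at least one significant interaction when tDCS adds nothing is 1 − 0.95^m:

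- m = 15: 1 − 0.95^15 = 0.537
- m = 13: 1 − 0.95^13 = 0.487
- m = 9: 1 − 0.95^9 = 0.370
- m = 27, if EMG is analysed: 1 − 0.95^27 = 0.750

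**Correlated tests.** Outcomes in the same person are correlated, and the documents give no values. Assuming one common correlation, simulation of two-sided z tests (200,000 draws) gives:

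| Tests | 0.3 | 0.5 | 0.7 | 0.9 |
|---|---|---|---|---|
| 15 | 46% | 36% | 25% | 14% |
| 13 | 42% | 34% | 24% | 14% |
| 9 | 33% | 27% | 20% | 12% |

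**The plan's own test.** Simulating the 2 × 3 interaction F test (2 and 116 df, 30 per group, assumed within-person correlation 0.6, 24,000 trials) gives nearly the same:

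| Tests | 0 | 0.3 | 0.5 | 0.7 | 0.9 |
|---|---|---|---|---|---|
| 15 | 54% | 46% | 37% | 27% | 15% |
| 9 | 37% | 33% | 28% | 21% | 13% |

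With 20 per group and 15 tests, the values at correlations 0, 0.5 and 0.7 are 54%, 37% and 27%. Only interactions are counted; the ANOVA main effects are left out.

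**The case against.** **The count is inferred.** Section 7 names three outcome groups. Read as only three tests, the chance is 1 − 0.95³ = 14% if independent, 11% at correlation 0.7 and about 8% at 0.9. Averaging static balance over stance as well gives 8 tests: 34% if independent and 19% at 0.7. The point stands as far as precision goes. But no composite per domain is defined, so three tests is the least likely reading, and it still exceeds 5%.

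**The upper end is too high.** Independence is implausible for three SEBT directions on one limb, or for MEPs at two intensities in one session, and a single common correlation is a simplification. This is fair: 54% is an upper bound for 15 tests and not a best estimate. The title range also leaves out correlation 0.9, where the values are 12–15%.

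**The plan does not say that one significant result is enough.** The Background hypothesis can be read as requiring all three domains, and then the figure above would not be the error rate of the conclusion. But the plan does not adopt that rule either. The absence of any success criterion is part of the defect.

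**This is a dissertation project whose objective is to investigate an effect.** Separate tests labelled exploratory would be defensible in such a study. The plan does not label them so; it describes a randomised, sham-controlled trial of efficacy.

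**Figure 2 cannot be read**, so the statement that the number of tests is not given applies to the readable text. The accompanying text describes the same testing days without ranking the outcomes.

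**Conclusion.** The concern holds. Section 7 sets a rule, each outcome at 0.05, that does not limit the error of the efficacy conclusion, and nothing elsewhere in the readable text repairs it. For 9 to 15 tests and assumed correlations from 0 to 0.7, the chance of at least one false significant interaction is about 20% to 54%. The count is a reading of the Outcome Measures text and the correlations are assumptions, so the exact size is uncertain. The direction is not: every count and correlation examined gives more than 5%. This must be fixed before unblinded analysis, because a primary outcome chosen after the results are known would not be credible.

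**What to change.** Amend section 7 before any unblinded analysis:

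1. Name one fully defined primary variable. If it is a static-balance variable, state the force-plate metric, stance and vision condition.
2. Name the contrast that decides it, either the overall interaction or the group difference in change at a stated test, at two-sided 0.05 (the overall F test has no sidedness).
3. Test a short list of key secondaries in a fixed order or with Holm.
4. Label all other variables exploratory and report them with estimates and confidence intervals.
5. Restate the sample-size justification in section 15 for the same primary.

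Which variable is primary is the sponsor's choice. One prespecified primary test returns the false-positive rate of the main claim to 5%. For comparison, Bonferroni over all outcomes would require 0.05/15 = 0.0033 or 0.05/9 = 0.0056 per test.

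The cost is protocol wording, with no extra data. Results outside the primary and key secondaries could be reported only as exploratory, and Holm costs some power on the secondaries. If the primary is not a corticospinal measure, f = 0.55 may not apply. Item 5 can then be met by stating what the planned number can detect, without enrolling more.

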#### Figure 1. Flowchart of Overall Study Design and Procedure

There will be one screening day and 2 separate testing days (Figure 2). On the screening day, participants will fill out the CAIT and health questionnaire to determine the presence of CAI. On the first testing day, self-reported function (FAAM), static postural control, and neural excitability (H-reflex, TMS) will be measured. On the second testing day, dynamic postural control (SEBT and side hop) will be measured. The testing days will be separated by at least 24 hours (Figure 2). The testing will repeat at post-2-weeks and post 4-weeks of intervention measurement.

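### The 2x3 repeated-measures ANOVA is valid but does not adjust for the pre-test, plans no arm difference with a confidence interval, and leaves its Sidak comparisons undefined; a baseline-adjusted joint test is a cheap improvement

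*Combined protocol and SAP*

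**What the plan says.** Section 7 (Data Management) holds the whole analysis plan. Each outcome gets a 2 "by 3 (time: preintervention, 2 weeks post-, 4 weeks post-intervention) ANOVA with repeated measures will be performed", and this model "will be performed to determine effects of tDCS for each outcome measure". The pre-intervention value is therefore a level of the time factor. No section mentions a baseline covariate, an estimated difference between arms or a confidence interval.

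The follow-up is gated: "In the presence of a significant group-by-time interaction, a post-hoc analysis using Sidak adjustment will be conducted". The plan does not say which pairs are compared or how many comparisons the adjustment covers.

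Three other places bear on the point:
- Study Interventions: "All groups will receive the same progressive balance training (BT"), and "The 4 weeks of BT has been shown effective in enhancing postural control in patients with CAI".
- Visit timing: the text with Figure 1 says "The testing will repeat at post-2-weeks and post 4-weeks of intervention measurement", and Study Interventions says "BT will be implemented 3 times a week over 4 weeks".
- Section 15 (Local Number of Subjects): "The effect size (f=0.55) in this study was large". It plans 60 participants but speaks of 20 per group, while the Study Overview has two arms. The number per arm is thus 30 or 20.

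**The concern.** Two gaps sit side by side.

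**Efficiency.** Everyone has a pre-test. Using it as one of three outcome levels amounts to analysing changes. When the correlation between visits is low to moderate, this carries the noise of the pre-test into the comparison. A covariate removes only the part of the outcome that the pre-test predicts. If the true effect is moderate, some power is given up without need.

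**Specification.** A significant 2-df interaction does not say which arm did better, by how much, or when. The follow-up has to supply that, and it could mean several things: arms compared at two visits, arms compared at three visits, or time pairs within each arm. Because both arms receive training that the protocol itself calls effective, a within-arm change does not isolate tDCS. If the interaction is not significant, the plan yields no estimate of the arm difference at all.

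**Working it through.** **The plan's own figure.** Section 15 reports about 8 per group, 24 in total, at f=0.55, alpha 0.05 and power 0.80. This can be reproduced as a three-group, three-visit interaction with noncentrality f² × N × 2 and df 4 and 2(N−3). N=24 gives 0.3025 × 24 × 2 = 14.52 and power 0.836; N=21 gives 12.71 and 0.769. It rests on three groups and on options that the section does not state. It supplies no SD, correlation or time course.

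**Assumed inputs.** SD 1 at each visit; equal correlation rho between visits; complete data; two-sided 0.05; n=30 per arm, then 20. With d=0.5, the arm differences at (pre, first later visit, second later visit) are:
- sustained (0, 0.5, 0.5)
- gradual (0, 0.25, 0.5)
- late (0, 0, 0.5)

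**Planned interaction test.** F with df 2 and 2(2n−2), noncentrality (n/2) × (sum of squared centred arm differences)/(1−rho). For n=30 and rho 0.5:
- sustained: 15 × 0.1667/0.5 = 5.00, power 49.3%
- gradual: 15 × 0.125/0.5 = 3.75, power 38.3%
- late: 15 × 0.1667/0.5 = 5.00, power 49.3%

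**Baseline-adjusted joint test.** F with df 2 and 2n−4. Given the pre-test, each later value has variance 1−rho² and the two have covariance rho−rho². Noncentrality is (n/2) × δ′Σ⁻¹δ, reduced slightly for chance baseline imbalance (averaged over 2,000 baseline draws). At rho 0.5, Σ has 0.75 on the diagonal and 0.25 off it, so Σ⁻¹ has 1.5 and −0.5. Before the reduction:
- sustained: 15 × 0.50 = 7.50
- gradual: 15 × 0.34375 = 5.16
- late: 15 × 0.375 = 5.63

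For a sustained effect the ratio of the two noncentralities is 3/(1+2 rho): 1.50 at rho 0.5, 1.25 at 0.7 and 1.07 at 0.9.

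Power (%), planned / adjusted joint, d=0.5:

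| n per arm | rho | sustained | gradual | late |
|---|---|---|---|---|
| 30 | 0.5 | 49.3 / 65.4 | 38.3 / 48.7 | 49.3 / 52.4 |
| 30 | 0.7 | 72.4 / 80.3 | 59.1 / 65.0 | 72.4 / 73.2 |
| 30 | 0.8 | 88.8 / 91.7 | 77.7 / 80.5 | 88.8 / 88.6 |
| 30 | 0.9 | 99.6 / 99.6 | 97.6 / 97.7 | 99.6 / 99.5 |
| 20 | 0.5 | 34.1 / 45.9 | 26.4 / 33.0 | 34.1 / 35.6 |
| 20 | 0.7 | 53.2 / 60.1 | 41.6 / 45.5 | 53.2 / 52.8 |
| 20 | 0.8 | 71.8 / 75.1 | 58.5 / 60.3 | 71.8 / 70.3 |

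Simulation of the null at n=30 and rho 0.5 gives 4.9% rejection for both tests.

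**Large effect.** With two equal groups, f=0.55 corresponds to d = 2 × 0.55 = 1.1 SD. At rho 0.5 the planned test then has 97.2 to 99.5% power at 30 per arm (joint 99.4 to 100%) and 87.3 to 95.1% at 20 per arm (joint 94.2 to 99.0%).

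**Unequal correlation.** Under AR(1) correlation of 0.8, n=30 and a gradual effect, simulation gives the joint test about 57 to 58%. The uncorrected planned F has 62 to 63%, and the Greenhouse-Geisser version 59 to 60%. The uncorrected F rejects slightly more than 5% under the null (5.5 to 6.2% across runs). For sustained, fading and late effects under the same correlation, the joint test is ahead of both versions.

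**Sidak levels.** 1−0.95^(1/k) is 0.0253 for two comparisons, 0.0170 for three and 0.0085 for six. The unstated family therefore moves the per-comparison threshold threefold.

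**The case against.** The strongest reply is that nothing here is an error. The confirmatory test is named, is valid under randomisation and holds its level. Replacing it is a choice of efficiency, and the gain rests on inputs that the documents do not give. That stands. For a late effect the gain is about 3 points at rho 0.5 and roughly zero or slightly negative from rho 0.7 upward. On the protocol's only effect size, read as 1.1 SD with 30 per arm, there is little left to gain.

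It is also fair that follow-ups run only after a significant interaction, so a between-arm finding already exists by then. An omnibus test with no single significant visit is ordinary, and the joint test can end the same way.

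A reader might infer three stronger things that the documents do not support:
- **That the planned test is biased or invalid because the pre-test is an outcome level.** It is neither. The slight excess of rejections seen under AR(1) correlation concerns the uncorrected F and a correlation pattern that is itself assumed.
- **That the open follow-up would usually turn the result into improvement in both arms.** Given a significant interaction (sustained effect, rho 0.5, 30 per arm, level 0.0170), the chance that both arms show a significant change from pre-test to the second later visit depends on the assumed common training gain. It is about 1% at 0 SD, 22% at 0.4, 41% at 0.5 and 93% at 0.8. The documents give no such gain.
- **That the visit descriptions plainly contradict each other.** The Figure 1 wording can be read as weeks counted within the four-week programme, and the section 7 wording as weeks after it. They are ambiguous and need reconciling.

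**Conclusion.** The point holds as a cheap improvement in efficiency and specification, not as a correction of an error. At a 0.5 SD effect, equal correlation and 30 per arm, the adjusted joint test gains about 16, 10 and 3 points at rho 0.5 (sustained, gradual, late) and about 8, 6 and 1 at rho 0.7. At rho 0.8 to 0.9 it ranges from a gain of about 3 points to a trivial loss. At 20 per arm the pattern is similar with smaller gains, and the largest loss in the table is 1.5 points.

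The specification gap does not depend on these assumptions: no arm difference with an interval is planned, and the Sidak family is undefined. The undefined family and the unclear timing are supporting points. Confidence is medium, because SD, correlation and time course are all assumed. Multiplicity across the many outcomes is a separate matter that this change does not settle.

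**What to change.** For each outcome:
- Model the two later values with baseline, arm, visit, arm × visit and baseline × visit, using unstructured covariance and a named small-sample degrees-of-freedom method. Include every randomised participant with at least one later value.
- Use the joint 2-df test of the adjusted arm difference at the two visits in place of the interaction test.
- Report the adjusted arm difference with 95% CI at each later visit, whether or not the joint test is significant.
- State that these two between-arm differences are the Sidak family (0.0253 each) and that within-arm changes are descriptive.
- Reconcile the visit timing in the Figure 1 text, Study Interventions and section 7, so that the two later visits are defined.

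If a single contrast is preferred, name it before analysis and state its weakness. At 0.5 SD, rho 0.5 and 30 per arm, the second later visit alone has 19% power against 38% for the planned test if the effect fades from 0.5 to 0.25 SD. The mean of both visits has 27% against 49% if the effect is late.

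Cost: no new visits, data or software, only a few written sentences. Power can fall by up to about 2 points at high equal correlation. In the AR(1) gradual case it falls by about 2 points against the Greenhouse-Geisser-corrected test and about 5 against the uncorrected one. The power figures are for complete data. Without a small-sample correction the mixed-model Wald F has size 5.3% at 30 per arm and 5.4% at 20, which is why the method should be named.
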